Extent of exposure to study treatment will be summarized for the all treated patients population by study phase and cohort or treatment group. The number of infusions received, the total dose received (cells) and dose intensity will be summarized using descriptive statistics. The dose intensity is defined as the total dose received divided by number of infusions received.

7.5.2 *Adverse Events*

Treatment-emergent AEs will be summarized by study phase and cohort or treatment group. Events reported with a partial onset date (eg, month and year are reported but the day is missing) will be considered to be treatment-emergent if it cannot be confirmed that the event onset was prior to the first dose of study drug based on the available date entries.

Verbatim terms on case report forms will be mapped to preferred terms and system organ classes using the Medical Dictionary for Regulatory Activities (MedDRA, version 25.0 or higher).

Summaries that are displayed by system organ class and preferred terms will be ordered by alphabetic order of system organ class and by descending incidence of preferred term within each system organ class. Summaries displayed by preferred term only will be ordered by descending incidence of preferred term. Summaries of the following types will be presented:

- Overall summary of number of unique TEAEs and treatment-emergent serious adverse events (SAEs) and patient incidence of TEAEs meeting various criteria;
- Patient incidence of TEAEs by MedDRA system organ class (SOC), MedDRA preferred term and maximum CTCAE severity grade;
- Patient incidence of TEAEs by maximum CTCAE severity grade and MedDRA preferred term;
- Patient incidence of TEAEs related to study drug by maximum CTCAE severity grade and MedDRA preferred term;
- Patient incidence of treatment-emergent SAEs by maximum CTCAE severity grade and MedDRA preferred term;
- Patient incidence of treatment-emergent SAEs by SOC, MedDRA preferred term, and maximum CTCAE severity grade;
- Patient incidence of treatment-emergent SAEs related to study drug by maximum CTCAE severity grade and MedDRA preferred term;
- Patient incidence of Grade ≥ 3 TEAEs by maximum CTCAE severity grade and MedDRA preferred term; and

- Patient incidence of Grade ≥ 3 TEAEs related to study drug by maximum CTCAE severity grade and MedDRA preferred term.

At each level of summarization (eg, any AE, system organ class, and preferred term), patients experiencing more than one TEAE will be counted only once. In the summary of TEAEs by severity grade, patients will be counted once at the highest severity reported at each level of summarization.

Adverse event data will be presented in data listings by study phase, patient, cohort or treatment group, and event.

Some sensitivity analyses may be performed for Group 1 to summarize all TEAEs (ie, patient incidence of TEAEs by MedDRA preferred term) that occurred on or after date of randomization.

7.5.3 *Deaths, Other Serious Adverse Events, and Other Significant Adverse Events*

All deaths during the study, including the post treatment follow-up period, will be listed by patient, to include the primary cause of death. Serious AEs and other significant AEs, including those that led to withdrawal, interruption, or dose reduction of the study drug, will be provided in separate patient data listings.

The number and percentage of patient deaths, as well as primary cause of deaths will be summarized by study phase and cohort or treatment group.

All deaths within 30 and 60 days of the last dose of MT-401 will be summarized. For Group 1 SOC arm, deaths within 30 days and 60 days of randomization date plus average time from randomization to last dose in the MT-401 arm will also be summarized as reference.

7.5.4 *Clinical Laboratory Evaluation*

All descriptive summaries of laboratory results will be based on data collected by local laboratories and collected on the eCRF. All data will be included in by-patient data listings. Laboratory measurements identified as abnormal (ie, outside the normal range) will also be listed separately by study phase, patient, treatment group, laboratory test, and unit. In addition, normal ranges will be presented in a separate listing.

Clinical laboratory measurements, including hematology, serum chemistry, and coagulation, will be summarized by study phase and cohort or treatment group. Descriptive statistics will be presented for observed values and changes from baseline at each visit where parameters were scheduled to be collected per the clinical study protocol.

Where applicable, laboratory results for select parameters will be assigned a toxicity grade based on the U.S. Department of Health and Human Services *Common Terminology Criteria for Adverse Events (CTCAE)*, version 5.0 (27 Nov 2017). If the quantitative criteria for grading are equivalent for two grades and the differentiation is described by clinical interventions, the clinical intervention component will not be considered and the highest CTCAE grade will be assigned. Similarly, death related to AE (ie, Grade 5) cannot be determined with available laboratory-based

data collection and, thus, will not be summarized as a category. Laboratory parameters that include multiple sets of criteria for each direction (eg, separate criteria for potassium measures to assess hyperkalemia and hypokalemia) will be summarized separately to reflect each set of criteria.

Five-by-five contingency tables will be presented for lab tests where toxicity grading can be applied, to summarize the shift from the baseline grade to the worst post-baseline grade. Grades will be presented as none (Grade 0; ie, measurements did not meet any CTCAE criteria for Grades 1 through 4), mild (Grade 1), moderate (Grade 2), severe (Grade 3), or life-threatening (Grade 4). Summary results will include the count and percentage of patients within each shift category. In addition, a table will be presented to include the count and percentage of patients with at least one post-baseline Grade 3 or higher toxicity by laboratory parameter.

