Patients are excluded from the study if any of the following criteria apply:

- 1. Clinically significant or severely symptomatic intercurrent infection
- 2. Pregnant or lactating
- 3. Any other issue which, in the opinion of the treating physician, would make the patient ineligible for the study
- For Group 1, anti-neoplastic therapy after HSCT and prior to or during dosing of MT-401
- 5. For Group 2, concomitant anti-neoplastic therapy during or after dosing of MT-401
- 6. Evidence of a cute or chronic GVHD≥Gra de 2 (exception: a cute or chronic Gra de 2 GVHD of skin a llowed if stable) within one week prior to receiving MT-401
- 7. Taking systemic corticosteroids (exception: physiological doses of steroids a llowed)
- 8. On other investigational therapy post-HSCT
- 9. Anti-thymocyte globulin or Campath within 28 days of MT-401 infusion

Donor Inclusion Criteria:

Donors for a llogeneic stem cell transplants must be considered suitable for and consent to stem cell donation, as per the standard operating procedures of the stem cell transplant program. If a donor has been chosen for the transplant, that same donor will also be used to manufacture the T cell product provided that there are no new reasons for ineligibility since the stem cell collection. The donors will be evaluated as per standard institutional guidelines. The donor clearance by the National Marrow Donor Program (NMDP) is also acceptable.

Leukapheresis material will be collected from the same HSCT donor to manufacture MT-401 for the patient.

Dosage and Route of Administration

A dose of 50×10^6 cells (flat dosing) will be the dose explored in the Safety Lead-in portion for this study with a minus 1 (-1) dose level of 25×10^6 cells (flat dosing), should the need arise to de-escalate. For the Phase 2 portion of the study, the dose administered is 100×10^6 cells (flat dosing). Cohort III will evaluate a higher dose (200×10^6 cells [flat dosing]) of MT-401 than that used in the Phase 2 portion of the study. Initially, following the completion of Cohorts I and II, patients in Groups 1 and 2 of the Phase 2 portion of the study will receive three consecutive flat doses of 100×10^6 cells each, at intervals of at least 2 weeks. MT-401 will be given by IV infusion through either a peripheral or central line. The patients will be monitored for 1 hour post-infusion as outpatients.

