4.3.1. Safety Lead-in Portion of the Phase 2 Study

The Safety Lead-in portion includes two cohorts (Cohort I and Cohort II) that will evaluate the safety profiles of MT-401 manufactured with peptide pools obtained from two different vendors (JPT versus Almac). Therefore, Cohorts I and II may be enrolled in parallel. Approximately 3-6 patients closely fitting the eligibility criteria of active disease (Group 2) will be infused with MT-401 in each of Cohorts I and II to determine the safety of patient-specific product consisting of 50 x 10⁶ cells (flat dosing) every 2 weeks for a total of 3 doses using the standard 3+3 design (Section 4.5). A minus 1 (-1) dose level of 25 x 106 cells (flat dosing) may be used should the need arise to de-escalate (Section 4.3). All patients treated will be observed for 28 days from the day of the initial MT-401 infusion before safety is established. If no differences in the safety are noted between the peptide vendors, then it will be concluded that the change in peptide manufacturer is not relevant to dosing and the main portion of the Phase 2 study will be initiated with the product utilizing Almac peptides.

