A minimum of 3 patients each will be treated in Cohorts I and II; if 1 patient experiences a DLT related to MT-401, 3 additional patients will be treated in the cohort (see Section 5.6). If overall, 0 out of 3 patients or 1 out of 6 patients experience a DLT in the specific cohort, this dose will be established as safe for the Phase 2 portion of the study (see Section 5.6). Additional patients may be treated to acquire data such as biomarkers as long as no safety issues arise. In the event that > 1 patient, experiences a DLT (see Section 5.6) related to MT-401, then no further patients will be treated in that cohort. A new cohort of patients will be treated at a lower dose level (DL1) with a flat dose of 25 x 10⁶ cells (Cohorts -I or -II). Dose Level 1 will be repeated with an additional 3-6 patients once new peptides are synthesized for use during manufacturing (Cohort II). If Cohort II is deemed safe for patients, this dose and peptide manufacturer will be used in the Phase 2 portion of the study. In parallel to opening the Phase 2 portion of the study, Cohorts III-V will open to enroll patients using the same standard 3+3 design described above for Cohorts I and II.

Patients who initially receive any dose of MT-401, but are subsequently deemed unevaluable (e.g., important protocol deviation, starting investigational drugs not approved by the Sponsor) and removed from the study will not count as DLTs in the Safety Lead-in and Cohorts III-V and may need to be replaced.

Confidential Page 33 of 74

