6.3 Treatment

6.3.1 *Treatment Administered*

MT-401 will be administered as a patient-specific product every 2 weeks for 3 doses. MT-401 will be given by intravenous (IV) infusion through either a peripheral or central line. The patients will be monitored for any safety concerns for 1 hour post-infusion as outpatients.

A dose of 50×10^6 cells (flat dosing) will be the dose explored in the Safety Lead-in portion for this study with a minus 1 (-1) dose level of 25×10^6 cells (flat dosing), should the need arise to de-escalate. The Safety Lead-in portion of the study, specifically, tests safety of MT-401 manufactured with peptides produced from different vendors (JPT/Almac).

Following completion of the Safety Lead-in portion the study will proceed to open Groups 1 and/or 2 of the Phase 2 study at the highest cleared dose of 100×10^6 cells (flat dosing) from the Phase 1 trial.

In parallel to the opening of Groups 1 and/or 2, Cohort III will test the flat dose equivalent of 200×10^6 cells. If the 200×10^6 cells dose being tested in Cohort III is noted to be safe, then the patients enrolled, but not yet treated, in Groups 1 and 2 may be treated at the 200×10^6 cells dose, unless the Sponsor decides to remain at the current dose of 100×10^6 cells.

Cohorts IV and V will evaluate the safety of MT-401 manufactured using the accelerated method at doses of 100×10^6 and 200×10^6 cells, respectively. A lower dose level of 50×10^6 cells (flat dosing) may be used should the need arise to de-escalate. At the conclusion of Cohorts IV and V, which evaluate the safety of the product manufactured using an accelerated process at two different doses, the Sponsor may change the Phase 2 dose to the dose deemed to be safe for MT-401 manufactured using the accelerated process.

6.3.2 *Method of Assigning Patients to Treatment Groups*

Patients in the Safety Lead-in (Cohorts I and II) and Cohorts III-V will not be randomized.

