intermediate, unfavorable), present genetic abnormalities, bridging therapy (yes/no), number of lines of prior systemic therapy, prior cell therapy, and prior radiation therapy. Detailed summary of prior anti-cancer therapy will be provided for prior systemic therapy (excluding bridging therapy) and bridging therapy separately.

Demographic, baseline characteristics, and disease history characteristics will be summarized by study phase and cohort or treatment group for the all treated patients population. For Group 1, summaries will be repeated for the all randomized patients population and the PP population.

If an imbalance of more than 20% between the MT-401 and SOC arms is observed among the age, genetic mutations, transplant donor type, conditioning regimen, or complete remission status prior to transplant, the primary analysis may be modified to stratify for these factors.

Medical history data will be presented in patient data listings by study phase and patient.

7.4.3 *Measurements of Treatment Compliance*

Compliance to the study treatment regimen will be determined as the total dose received divided by the expected dose received, multiplied by 100. The total dose received will be calculated as the sum of actual dose received for each of the 3 planned doses. The expected dose received will be determined as the sum of the planned dose for each of the 3 doses (ie, 150×10^6 cells). Dosing compliance will be summarized using descriptive statistics, by study phase and cohort or treatment group, based on the all treated patients population. The number and percentages of patients who are < 66.6% compliant and \geq 66.6% compliant will be summarized.

7.4.4 *Primary Efficacy Endpoint Analysis Methods*

Phase 2 Adjuvant (Group 1):

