The primary endpoint of RFS for Group 1 will be tested at $\alpha = 0.05$ (two-sided) at the final analysis. The analysis of RFS at the interim analysis will be performed for the purposes of testing for futility and possible re-estimation of sample size as described in [Section 7.4.7.3](#). Analysis at the interim and final analysis will be performed based on ([Chen et al. 2004](#)) in order to maintain the type 1 error at $\alpha = 0.05$ for RFS at the final analysis.

Secondary endpoints for Group 1, OS and GRFS, will be presented for descriptive purposes only and no adjustments will be made for multiplicity.

The primary endpoint of CR for Group 2 will be tested at $\alpha = 0.05$ (two-sided) at the final analysis. DOCR will be presented for descriptive purposes only and no adjustments will be made for multiplicity.

7.4.7.6 *Use of an “Efficacy Subset” of Patients*

The primary efficacy analysis for Group 1 will be performed on all randomized patients and the PP population will be utilized as a sensitivity analysis. The PP population will exclude patients received less than two-thirds of total planned dose or had other major protocol deviations.

7.4.7.7 *Examination of Subgroups*

Subgroup analyses may be conducted based on, but not limited to, the covariates defined in [Section 7.4.7.1](#).

For time to event endpoints forest plots of the event-free rates at landmark times may be generated to display the outcomes in subgroups. Additionally, Kaplan-Meier plots with subgroup KM curves overlaid on the same plot may be presented. For binary endpoints, the rates within subgroups may be presented in forest plots.

7.5 **Safety Evaluation**

Safety analysis will be carried out for the all treated patients population, to include all patients who receive at least one dose of study drug. Patients who do not complete the study, for whatever reason, will have all available data up until the time of termination included in the analysis. For safety analysis presented by study visit, the baseline value will be defined as the last value reported prior to first study drug administration.

7.5.1 *Extent of Exposure*

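### SAP 7.4.3 prints an expected total dose of 150 × 10⁶ cells, which fits only the 50 × 10⁶ cohorts; used in Phase 2, where 300 × 10⁶ is planned, it would double every compliance figure

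*SAP*

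**What the plan says.** SAP 7.4.3 (Measurements of Treatment Compliance) defines compliance as total dose received over expected dose, times 100. On the denominator it says: "The expected dose received will be determined as the sum of the planned dose for each of the 3 doses". A parenthesis introduced by 'ie' then gives the value as 150 × 10⁶ cells. No other value is given for any cohort or group.

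The scope is the whole study: "Dosing compliance will be summarized using descriptive statistics, by study phase and cohort or treatment group, based on the all treated patients population". Patients are also split at 66.6% compliance.

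The Phase 2 dose is not 50 × 10⁶. SAP 6.3.1 says that "the study will proceed to open Groups 1 and/or 2 of the Phase 2 study at the highest cleared dose of" 100 × 10⁶ cells. The protocol synopsis agrees: "For the Phase 2 portion of the study, the dose administered is" 100 × 10⁶ cells. Protocol 4.3.2 and Table 5 give the same dose, and both documents allow a later switch to 200 × 10⁶.

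Two other SAP sections bear on the point. Section 7.4.7.6 says: "The PP population will exclude patients received less than two-thirds of total planned dose or had other major protocol deviations". It gives no figure and does not refer back to 7.4.3. Section 7.5.1 (Extent of Exposure) says: "The number of infusions received, the total dose received (cells) and dose intensity will be summarized using descriptive statistics".

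**The concern.** The rule in words and the number in the parenthesis disagree for every patient not dosed at 50 × 10⁶ per infusion, which includes all of Phase 2. The SAP does not say which prevails.

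With full infusions and the correct denominator, the 66.6% cut separates patients given one infusion from those given two or three. With 150 × 10⁶ in Phase 2 it separates nobody who received a full infusion. Under-dosing is foreseen in this trial. Product with fewer cells may be given (protocol 4.1), manufacturing limits may change the dose (Table 5 footnote c, section 6.6), and treatment stops on progression (section 7.1). A compliance table that cannot show under-dosing fails at its purpose.

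**Working it through.** **Inputs.** Three planned infusions (SAP 6.3.1). Dose per infusion from protocol Table 4, and for Phase 2 from protocol 4.3.2 and SAP 6.3.1. Printed denominator 150 × 10⁶ and cut of 66.6% from SAP 7.4.3. All doses below are in units of 10⁶ cells.

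**Reproducing the printed figure.** Expected total = 3 × dose per infusion. 3 × 50 = 150, so the figure is right at the 50 level. The other levels give 3 × 25 = 75, 3 × 100 = 300 and 3 × 200 = 600.

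**Compliance after 1, 2 and 3 full infusions.** With the printed figure it is 100 × (infusions × dose) / 150. With the worded rule it is 100 × (infusions × dose) / (3 × dose), which is 33.3%, 66.7% and 100% at every level.

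| Dose per infusion | Where planned | Planned total | Using 150: 1 / 2 / 3 infusions |
|---|---|---|---|
| 25 | Cohorts -I, -II (only if de-escalated) | 75 | 16.7% / 33.3% / 50% |
| 50 | Cohorts I, II; -IV (only if de-escalated) | 150 | 33.3% / 66.7% / 100% |
| 100 | Phase 2 as opened; Cohort IV | 300 | 66.7% / 133.3% / 200% |
| 200 | Cohorts III, V; Phase 2 if switched | 600 | 133.3% / 266.7% / 400% |

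**Effect on the cut.** 0.666 × 150 = 99.9. A single full infusion of 100 exceeds this. As a share of the true plan, the cut falls to 99.9/300 = 33.3% at the 100 level and 99.9/600 = 16.65% at the 200 level. At the 25 level the error runs the other way: a fully dosed patient shows 50% and is counted below the cut.

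**Reduced infusions.** A Phase 2 patient given three infusions of 50 instead of 100 would show 150/150 = 100%. The true value is 150/300 = 50%.

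**Per-protocol rule, only if 150 is reused there.** Two-thirds of 150 is 100, so an Arm A patient with one infusion of 100 is not below the limit and stays in. Two-thirds of 300 is 200, so under the plain meaning of planned dose the same patient is excluded.

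**Number of patients.** The Phase 2 part of the table covers about 75 (Arm A) + 60 (Group 2) = 135 planned MT-401 patients.

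**The case against.** The strongest reply is that the operative rule is the sentence, not the parenthesis. The sentence gives 300 × 10⁶ for Phase 2, and a programmer who follows it makes no error. The 150 is probably a leftover: the amendment history records a dose of 50 × 10⁶ before Phase 2 was raised to 100 × 10⁶. Values of 200% or 400% would be conspicuous, and SAP 6.5 requires independent programming and senior review. The same facts are reported correctly elsewhere: completion of all three doses with reasons (SAP 7.3.1), and infusions and total dose (SAP 7.5.1).

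Most of this stands, and it limits the severity. It does not remove the defect. 'Ie' equates the two quantities, so the text contradicts itself, and two independent programmers could each follow a different half of it. The 200% would be noticed, but 66.7% after one infusion looks like a correct value for two.

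A reader might infer that the per-protocol sensitivity analysis is compromised. The documents do not support that. SAP 7.4.7.6 refers only to total planned dose, which on its plain meaning excludes the one-infusion patient. The harm needs the further assumption that 150 is reused. Exclusions are also to be listed with reasons (SAP 7.4.1).

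**Conclusion.** The printed denominator is wrong as written for every planned dose other than 50 × 10⁶. If it is used, compliance is overstated twofold at 100 × 10⁶ and fourfold at 200 × 10⁶, and is halved at 25 × 10⁶ if those cohorts open. At 100 or 200 × 10⁶, the 66.6% split then passes anyone given a single full infusion.

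These figures assume full infusions at the planned dose and that the parenthesis, not the sentence, is programmed. The documents do not settle which would happen, so it would go too far to say that the compliance table will be wrong.

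The direct effect is limited to one descriptive summary. A reader might also suspect an effect on the efficacy conclusion. There is none: the primary RFS analysis uses all randomized patients as defined in SAP 7.2, and no test, endpoint or interim rule uses compliance. The point is minor and should be corrected.

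**What to change.** 1. In SAP 7.4.3, replace the parenthesis with: *(ie, 3 × the protocol-planned dose per infusion for the patient's cohort, or for the Phase 2 regimen in force at the patient's first infusion: 75, 150, 300 or 600 × 10⁶ cells for the 25, 50, 100 or 200 × 10⁶ levels; not reduced for manufacturing shortfall)*.

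2. In SAP 7.4.7.6, write: *less than two-thirds of the total planned dose as defined in Section 7.4.3*.

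Naming the regimen at first infusion matters because patients enrolled but not yet treated may be moved to 200 × 10⁶ (protocol 4.3.3 and 4.3.4). Ruling out a reduction for shortfall matters because a denominator that shrinks with the product supplied would hide the under-dosing that the table should show.

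The cost is one replaced parenthesis and one cross-reference. No new data, patients or design change are needed.
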